6.11.2. Dose-limiting toxicity

In Part A, frequency distributions of patients who experienced any DLTs during Cycle 1 will be summarized by cohort using the DLT population. A listing of DLTs will be produced.

6.11.3. Adverse Events

The available latest version of Medical Dictionary for Regulatory Activities (MedDRA) will be utilized for categorizing to System Organ Class (SOC) and Preferred Term (PT). National Cancer Institute (NCI) - Common Terminology Criteria for Adverse Events (CTCAE) Version 4.03 will be referred for identifying grade and/or relevant event term.

Treatment-emergent adverse events (TEAEs) are defined as events that first occurred or worsened in severity after/on the first infusion of the study drug.

Adverse events will be summarized by CTCAE term and MedDRA term.

The summary by MedDRA term would be primary for the study report. For the FAS population, the following summaries will be provided by part and cohort:

- An overview of AEs
- Summary of TEAEs by SOC and PT
- Summary of TEAEs by PT
- Summary of TEAEs by SOC, PT and Maximum Grade

These analyses will be repeated for AEs related to study drug. Also, a listing of AEs will be prepared.

Using CTCAE term, TEAEs by CTCAE SOC, CTCAE Term and Maximum Grade will be summarized.

6.11.4. Deaths, Serious Adverse Events, and Other Significant Adverse Events

All deaths that occur after the first infusion of the study drug together with primary cause of death will be listed based on the FAS population.

The following items for AEs leading to death will be provided:

- Summary of AEs leading to death by PT
- Summary of AEs leading to death related to study drug by PT
- Listing of AEs leading to death

For the FAS population, the following items for treatment emergent SAEs will be generated:

- Summary of SAEs by PT
- Summary of SAEs related to study drug by PT

- Listing of SAEs

As other significant AEs, the following items will be provided:

- Summary of AEs leading to olaratumab discontinuation by PT
- Summary of AEs leading to doxorubicin discontinuation by PT in Part A
- Summary of AEs leading to olaratumab delay/omission/reduction/interruption by PT
- Summary of AEs leading to doxorubicin delay/omission/reduction/interruption by PT in Part A

The above four items will be repeated for AEs related to study drug. Also, a listing of AEs leading to study drug discontinuation (olaratumab or doxorubicin in Part A and olaratumab in Part B) will be prepared.

6.11.5. Clinical Laboratory Evaluation

Laboratory results will be graded according to NCI-CTCAE Version 4.03, when applicable. Grading will be purely based on the numeric results and no investigator's assessment will be considered. Laboratory values will be converted to standard units. The laboratory results not corresponding to terms in NCI-CTCAE Version 4.03 will not be graded.

For the FAS population, shift tables of graded laboratory parameters from baseline to the worst value on the study will be generated by part and cohort.

For the FAS population, the laboratory results will be presented in a listing with a flag for values outside of the laboratory normal range. Laboratory reference ranges will be listed. Also, a line plot of the laboratory results will also be provided.

6.11.6. Vital Signs and Other Physical Findings

Listings of vital signs, physical examinations, and Eastern Cooperative Oncology Group performance status will be provided for the FAS population.

6.11.7. Electrocardiograms and Echocardiography

Three replicate electrocardiograms (ECGs) will be obtained at each time point. All parameters will be fully read at the first measurement and only RR interval, QT interval and heart rate will be read at the second and third measurements. The average of them will be used for analysis, if applicable. If missing values exist, the average will be derived without the missing values.

QT analyses will be performed with Bazett and Fridericia correction (QTcB and QTcF), respectively. QTcB and QTcF based on each read are calculated as follows:

- $QTcB = QT / RR^{1/2}$
- $QTcF = QT / RR^{1/3}$

6.11.7.1. PK matched ECG Data

The change will be calculated using the time-matched baseline for Cycle 1. Frequency distributions of patients who fulfill the following criteria will be summarized by part and cohort for the FAS population.

- QTc values: >450, >480, and >500 msec
- The change from baseline in QTc: >30 and >60 msec

Line plot of QTc values and their time-matched changes from baseline will be provided based on the FAS population.

Also, the time-matched changes will be plotted against the blood concentration of olaratumab by part and cohort for the FAS population. A linear regression model will be used to investigate the relationship between the QTc changes and the concentration of olaratumab and the fitted model and the 90% confidential interval will also be shown in the plot. It should be noted that, in Cohort 2 of Part A, ECG data at the sampling time of '0.5 h ± 5 min Postinfusion of doxorubicin' in both Cycle 1 and Cycle 3 will be excluded to avoid the effect of doxorubicin. Especially when olaratumab and doxorubicin will be administered on Day 8 in Cycle 3, additional sampling times ('1 h ± 10 min Postinfusion of olaratumab', '48 ± 6 h Postinfusion of olaratumab', '72 ± 6 h Postinfusion of olaratumab' and '168 ± 8 h Postinfusion of olaratumab') will be excluded.

ECG data including QTc values and their time-matched changes from baseline will be listed. A listing of blood concentration of olaratumab will be provided.

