5.4.4. Olaratumab Pharmacokinetics

Olaratumab serum concentration data are currently available from 2 Phase 1 studies, JGDC and JGDF, as well as from 5 Phase 2 studies, I5B-IE JGDA (JGDA), I5B-IE-JGDB (JGDB), I5B-IE-JGDE (JGDE), JGDG and I5B-IE-JGDH (JGDH). The serum concentration data available for Studies JGDA, JGDC, and JGDF were, however, generated using an enzyme-linked immunosorbent assay that was not fully validated. The quantitative PK results derived from the aforementioned 3 studies can therefore only be used as supporting evidence and will only be discussed briefly in the interest of completeness. The human serum assay has been subsequently optimized and validated and is being used to support all ongoing and future studies, including Study JGDK. Pharmacokinetic data were obtained using this validated serum assay from 4 Phase 2 studies, including Study JGDG.

In Study JGDG, olaratumab was tested at the dose of 15 mg/kg administered as a 60-minute infusion on Day 1 and 8 of a 21-day cycle and was tested in combination with doxorubicin in patients with STS. Steady state seemed to be reached during Cycle 3, and maximum observed concentration at steady state ($C_{max,ss}$) and minimum observed concentration at steady state

($C_{min,ss}$) ranged from 341 to 411 $\mu\text{g}/\text{mL}$ and from 113 to 121 $\mu\text{g}/\text{mL}$, respectively, across Cycle 3 to 6. A mean $t_{1/2}$ estimate of 6.7 days was obtained from 7 subjects after the second dose of Cycle 1. Individual $t_{1/2}$ estimates of 14.4 and 6.7 days were obtained after the second dose of Cycle 3. It should be pointed out that the $t_{1/2}$ estimates reported here are likely to be dependent on the duration of the sampling time, which never exceeds 168 and 336 hours after the first and second dose of each cycle, respectively.

Pharmacokinetic data in other Phase 2 studies may be found in Section 6 of the IB.

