- f In addition to the scheduled immunogenicity sampling, in the event of an infusion-related reaction, samples are to be collected as close to the onset of the event as possible, at the resolution of the event, and 28 days following the event.
- g Time-matched baseline ECGs (triplicates) will be taken within 4 days prior to Day 1 of Cycle 1, at the planned time for pre-infusion of olaratumab on Day 1.
- h If the second olaratumab administration in the cycle is delayed, olaratumab PK sampling and ECG will still be conducted at approximately 168 h postinfusion of olaratumab on Day 1. An additional olaratumab PK sample should then also be collected prior to the second olaratumab administration in the cycle.
- i If the second olaratumab administration in the cycle is delayed, the specified olaratumab PK sampling will be conducted based on the day of the second olaratumab administration in the cycle.
- j If the first olaratumab administration or the initiation of Cycles 2 or 4 is delayed, olaratumab PK and immunogenicity sampling and ECG will still be conducted at approximately 336 h (14 days) postinfusion of olaratumab on Day 8 of Cycles 1 or 3. An additional olaratumab PK sample should then also be collected prior to the first olaratumab administration in Cycles 2 or 4.
- k If the first olaratumab administration in the cycle is delayed, the specified olaratumab PK and immunogenicity sampling and ECG will be conducted based on the day of the first olaratumab administration in the cycle.
- l If doxorubicin administration is delayed, doxorubicin PK sampling on Days 1-3 will be conducted after the first, second, and third doses of doxorubicin in the cycle, respectively.

- m When only olaratumab is discontinued before Cycle 6 (doxorubicin continues for up to 6 cycles or until when a cumulative dose reaches), this PK and immunogenicity sampling and ECG will be taken at the nearest planned visit to 28 days after the last dose of olaratumab.
- n When enough data for the analysis of the primary and the secondary endpoints has been collected as determined by the sponsor and the patient has continued the study treatment for more than 3 years, PK samples and immunogenicity samples will no longer be collected.

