5.2. Determination of Sample Size

The study design requires 6 patients at each cohort in Part A for assessing the DLTs observed. This sample size was not based on a statistical power calculation.

In Part B, 6 patients are needed to evaluate PK and safety profile of olaratumab monotherapy. This sample size was estimated empirically based on other Phase 1 oncology studies. The estimation precision of PK parameters in this study is expected to be similar to that in previous studies (Study JGDC and Study JGDF), although there are no inter-subject variability data on a new assay.

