6.1.2. Data Analyses

All summary tables, figures and data listings will be produced by using the statistical packages SAS version 9.2 (or a more recent version).

Data will be summarized by part and cohort.

Baseline is defined as the last non-missing observation prior to the time of the first infusion of the study drug, unless otherwise stated. Observations on the same day of the first infusion of the study drug for which the time (hours and/or minutes) is missing and, according to the study schedule, to be collected prior to treatment, will also be considered baseline.

Descriptive statistics will include counts and percentages for categorical variables, and number of observations, mean, standard deviation, median, minimum and maximum for continuous variables unless otherwise stated.

Additional exploratory analyses of the data will be conducted as deemed appropriate.

The following data handling conventions will be applied in the analyses.

Study Day: Study day indicates the number of days the patient has been receiving study treatment. It is calculated as (assessment date)-(date of the first infusion of the study drug)+1 days if the assessment is done on or after the first infusion day of the study drug. If the assessment is done prior to the first infusion day of the study drug, study day will be calculated as (assessment date)-(date of the first infusion of the study drug). Date of the first infusion of the study drug is defined as study day 1.

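### The QTc–concentration regression ignores repeated ECGs within patients, so its 90% interval is too narrow; Cohort 1, with trough ECGs only, adds little, and a common-slope model with a patient effect should be added

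*SAP*

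**What the plan says.** SAP 6.11.7.1 specifies the model in one sentence: "A linear regression model will be used to investigate the relationship between the QTc changes and the concentration of olaratumab". The next clause adds that "the fitted model and the 90% confidential interval will also be shown in the plot", and the plot is the one for which the SAP says that "the time-matched changes will be plotted against the blood concentration of olaratumab by part and cohort for the FAS population". The regression sentence names no grouping of its own. Since the fit appears in a by-group plot and SAP 6.1.2 states "Data will be summarized by part and cohort", one fit per group is the natural reading. No patient effect, cohort term or pooled fit is mentioned. SAP 6.2 rules out covariate adjustment in every analysis.

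On size, SAP 5.2 states "The study design requires 6 patients at each cohort in Part A for assessing the DLTs observed" and plans six patients for Part B. It gives no power or precision basis for this regression. This SAP covers Cohorts 1 and 2 and Part B, that is 18 patients in three groups. Cohort 3 came with the later protocol amendment (a).

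On ECG timing, the Cohort 1 table in Protocol Attachment 4 is damaged in the text available, but its footnotes are clear by contrast with the other tables. Footnote g takes the Cohort 1 baseline ECG only "at the planned time for pre-infusion of olaratumab on Day 1". Cohorts 2 and 3 also have a baseline matched to 1 h after infusion, and Part B has two post-infusion baselines. Cohort 1 footnote i says "the specified olaratumab PK sampling will be conducted based on the day of the second olaratumab administration in the cycle", with no ECG; the Cohort 2/3 counterpart covers ECGs as well. The same contrast holds for footnote l on doxorubicin sampling. Cohort 1 ECGs therefore fall before dosing or at 168 h or 336 h after the preceding dose, apart from follow-up.

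**The concern.** There are two linked problems.

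First, ECGs from one patient are not independent. Each QTc change is taken from that patient's own baseline, so an error in that baseline is carried into every change that uses it. An ordinary regression counts six patients with 34 ECGs each as 204 independent observations. The interval it draws is then narrower than the data justify.

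Second, the question of whether olaratumab concentration moves QTc is the same in every group, yet it would be answered three times from about six patients each. One of those answers, Cohort 1, comes from a narrow band of trough concentrations. Separate small-sample slopes will differ by chance, and nothing in the plan tells the reader which to trust or that Cohort 1 covers troughs only.

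At stake is the credibility of the QTc statement in the study report, not a dosing or stopping decision: the SAP attaches no threshold or test to this regression.

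**Working it through.** The documents state no precision for this regression, so there is no figure to reproduce.

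**Inputs from the documents.** Six patients per group (SAP 5.2). From Protocol 5.4.4: steady-state peaks that "ranged from 341 to 411" ug/mL, troughs of 113 to 121 ug/mL, and half-lives of 6.7 days (mean of 7 subjects) and up to 14.4 days (one individual). ECG times from Attachment 4, read through Cycle 5: about 7 per patient in Cohort 1, 15 in Cohort 2 after the SAP's exclusion of the ECG 0.5 h after doxorubicin, and 34 in Part B.

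**Assumptions.** The documents give no QTc variability, and SAP 5.2 says there are no inter-subject data on the new assay. Base case: between/within-patient SD of QTc change 5/8 ms. Ranges: between 0 to 8 ms, within 8 to 12 ms, concentration CV 0 to 40%. Concentrations follow a one-compartment profile. Intervals use z = 1.645.

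**1. Interval with and without a patient effect, Part B.** At the mean concentration, with n = 6 patients, m = 34 ECGs each, and similar mean concentrations across patients:

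- Nominal (independence): 1.645 × √[(5² + 8²)/(6 × 34)] = 1.645 × √(89/204) = 1.1 ms.
- Actual: 1.645 × √[5²/6 + 8²/(6 × 34)] = 1.645 × √(4.167 + 0.314) = 3.5 ms.

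Away from the mean, slope uncertainty is added. At 411 ug/mL the simulated designs give about 1.4 to 1.7 ms nominal against 3.6 to 4.1 ms actual. The result depends on the assumed SDs (Part B, 411 ug/mL, CV 40%):

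| Between/within SD (ms) | Nominal | Actual |
|---|---|---|
| 0/8 | 1.4 | 1.4 |
| 5/8 | 1.7 | 4.1 |
| 5/12 | 2.4 | 4.5 |
| 8/8 | 2.3 | 6.5 |

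The understatement vanishes only if patients do not differ in mean QTc change.

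**2. Precision of the slope.** The olaratumab effect at a concentration C is slope × C, with 90% half-width 1.645 × SE(slope) × C. Take C = (341 + 411)/2 = 376 ug/mL, so the multiplier is 1.645 × 376 = 618.5. With a patient effect, SDs 5/8 ms and CV 25%:

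| Fit | SE (ms per ug/mL) | Half-width (ms) |
|---|---|---|
| Cohort 1 | 0.0226 | 14.0 |
| Cohort 2 | 0.0066 | 4.1 |
| Part B | 0.0046 | 2.8 |
| Common slope, 18 patients | 0.0036 | 2.2 |

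Separate cohort intercepts barely change the common-slope SE (0.0038 to 0.0039 at CV 40%). Varying half-life from 6.7 to 14.4 days, the CV and the modelling of the profile gives about 9 to 31 ms for Cohort 1, 2.9 to 3.8 ms for Part B, and 2.3 to 3.3 ms for the common slope with cohort intercepts. Adding Cohort 3 (24 patients) brings the last to about 2.0 to 2.6 ms.

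**3. How far Cohort 1 is from peak.** Against end-of-cycle troughs the peak is 341/121 = 2.8 to 411/113 = 3.6 times higher. Cohort 1 also has an ECG before the Day 8 dose. With a 6.7-day half-life that level is about 166 ug/mL, so the ratio is 411/166 = 2.5. At 14.4 days it is 1.5 to 1.7. Allowing patients to differ (CV 25%), the highest single Cohort 1 value is about 240 to 280 ug/mL, giving 411/280 = 1.5 to 411/240 = 1.7. At CV 40% it can reach 399 ug/mL, giving 411/399 = 1.0. The supportable range is 1.0 to 2.5.

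**The case against.** The strongest reply is that this is a descriptive plot in a Phase 1 study with no power basis and no decision attached. Part B is free of doxorubicin and has ECGs near peak. It already gives a half-width of about 4 ms or less in the base case, small beside the SAP's lowest QTc-change category of 30 ms. SAP 6.1.2 also allows further exploratory analyses, so a pooled fit is not forbidden in practice. The analyst may intend a patient effect and simply not have written it. All of this limits the importance of the point. It does not repair the interval as specified, and it does not tell the reader how to weigh Cohort 1.

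Three stronger readings are tempting and are not supported.

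- A reader might infer that the plan forces the Cohort 1 line to be extrapolated to more than twice its highest concentration. The SAP asks only for the line and interval in the plot, with no prediction at peak. The factor of two holds for a typical patient at a 6.7-day half-life, but not reliably against the highest individual value or at longer half-lives.
- A reader might infer that pooling is much more precise than every single fit. That is true against Cohort 1 only. The base-case gain over Part B is 1 − 0.0036/0.0046 = 22%. The gain is also in the slope: with cohort intercepts, the fitted Cohort 1 level at 411 ug/mL has a half-width of 4.3 ms, against 12.2 ms for Cohort 1 alone, but no better than Cohort 2 alone (4.3 ms).
- A reader might infer that the pooled fit should replace the others. In Part A, olaratumab accumulation and cumulative doxorubicin both increase over cycles. A cohort intercept cannot remove a doxorubicin effect that changes with time, and six-patient plots are a weak check of a common slope.

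**Conclusion.** The point stands as a modest but inexpensive improvement to the analysis. As written, the regression would draw an interval in Part B less than half as wide as it should be, provided between-patient SD in QTc change is about 5 ms; with no between-patient variation there is no error, and with 8 ms it is larger. Cohort 1 on its own cannot inform on peak exposure. A common slope makes better use of the same data, chiefly as a remedy for the weak Cohort 1 estimate.

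The SDs, CV and one-compartment profile are assumptions. The Cohort 1 timing rests on Attachment 4 footnotes because its table is damaged. With so few patients, a t quantile in place of z would widen the patient-effect intervals further.

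**What to change.** In SAP 6.11.7.1:

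- State that the QTc–concentration regression includes a patient random effect, in every fit whose interval is shown.
- Add one model across Part A and Part B with a common olaratumab slope, a separate intercept per cohort and a patient effect, applied after the doxorubicin-related exclusions. Report it beside the Part B-only fit, without ranking the pooled result above it.
- Keep the by-cohort plots, and note on the Cohort 1 plot that it covers trough concentrations only.

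In SAP 6.2, add an exception for the cohort intercepts. If the SAP is updated for Cohort 3, extend the ECG exclusions, which now name only Cohort 2, to that cohort too.

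The cost is SAP wording and one additional model; no new data are needed. The price of the pooled model is the common-slope assumption and possible confounding by doxorubicin over cycles, which is why the Part B fit must appear alongside it.

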10.1. General Considerations

The study design requires 6 patients at each cohort in Part A for assessing the DLTs observed. This sample size was not based on a statistical power calculation.

In Part B, 6 patients are needed to evaluate PK and safety profile of olaratumab monotherapy. This sample size was estimated empirically based on other Phase 1 oncology studies. The estimation precision of PK parameters in this study is expected to be similar to that in previous studies (Study JGDC and Study JGDF), although there are no inter-subject variability data on a new assay.

Statistical analysis of this study will be the responsibility of the sponsor.

The interpretation of the study results will be the responsibility of the investigator with the sponsor's CRP, pharmacokineticist, and statistician. The CRP and statistician will also be responsible for the appropriate conduct of an internal review for both the final study report and any study-related material to be authorized by Lilly for publication.

Any change to the data analysis methods described in the protocol will require an amendment ONLY if it changes a principal feature of the protocol. Any other change to the data analysis methods described in the protocol, and the justification for making the change, will be described in the clinical study report. Additional exploratory analyses of the data will be conducted as deemed appropriate.

Detailed information regarding the planned statistical analyses will be described in the Statistical Analysis Plan.

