f In addition to the scheduled immunogenicity sampling, in the event of an infusion-related reaction, samples are to be collected as close to the onset of the event as possible, at the resolution of the event, and 28 days following the event.

g Time-matched baseline ECGs (triplicates) will be taken within 4 days prior to Day 1 of Cycle 1, at the planned time for pre-infusion of olaratumab and 1 h ± 10 min postinfusion of olaratumab (approx. 2 h after pre-infusion of olaratumab) on Day 1.

h If the second olaratumab administration in the cycle is delayed, PK sampling for olaratumab and ECG will still be conducted at approximately 168 h postinfusion of olaratumab on Day 1 and PK sampling for doxorubicin will still be conducted at approximately 168 h postinfusion of doxorubicin on Day 1. An additional olaratumab PK sample should then also be collected prior to the second olaratumab administration in the cycle.

i If the second olaratumab administration in the cycle is delayed, the specified olaratumab PK sampling and ECG will be conducted based on the day of the second olaratumab administration in the cycle.

j If the first olaratumab administration or the initiation of Cycle 2 or 4 is delayed, olaratumab PK and immunogenicity sampling and ECG will be conducted at approximately 336 h (14 days) postinfusion of olaratumab on Day 8 of Cycles 1 or 3. An additional olaratumab PK sample should then also be collected prior to the first olaratumab administration in Cycles 2 or 4.

- k If the first olaratumab administration in the cycle is delayed, the specified olaratumab PK and immunogenicity sampling and ECG will be conducted based on the day of the first olaratumab administration in the cycle.
- l If doxorubicin administration is delayed, the specified doxorubicin PK sampling and ECG will be conducted based on the day of the doxorubicin administration.
- m When only olaratumab is discontinued before Cycle 6 (doxorubicin continues for up to 6 cycles or until when a cumulative dose reaches), this PK and immunogenicity sampling and ECG will be taken at the nearest planned visit to 28 days after the last dose of olaratumab.
- n When enough data for the analysis of the primary and the secondary endpoints has been collected as determined by the sponsor and the patient has continued the study treatment for more than 3 years, PK samples and immunogenicity samples will no longer be collected.

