29	4	1		Pre-infusion of olaratumab (Approx 336 h [14 days] postinfusion of olaratumab on Cycle 3 Day 8)	X	X		
			X					
30		8		Immediately postinfusion of olaratumab	X	X		
31			X	Pre-infusion of olaratumab	X ⁱ	X ⁱ		
32	5	1		Immediately postinfusion of olaratumab	X ⁱ	X ⁱ		
33			X	Pre-infusion of olaratumab	X	X	X	
34		8		Immediately postinfusion of olaratumab	X	X		
35			X	Pre-infusion of olaratumab	X ⁱ	X ⁱ		
36				Immediately postinfusion of olaratumab	X ⁱ	X ⁱ		
37	7, then every 2 cycles	1		Pre-infusion of olaratumab	X ^k	X ^l	X ^k	
38	Follow-Up			28-Day follow-up visit	X	X ^l	X	

Abbreviations: Approx. = approximately; ECG = electrocardiogram; h = hour; min = minute; PK = pharmacokinetics.

- a Pharmacokinetic Sample Number is numbered based on the case that olaratumab monotherapy is continued up to 7 or 8 cycles.
- b Olaratumab 15 mg/kg will be administered as an approximately 60-minute infusion.
- c Samples of approximately 3 mL of whole blood will be drawn into tubes. For the olaratumab samples, olaratumab serum PK measurements will be performed.
- d Electrocardiogram should be collected prior to any blood draws scheduled at the same time point.
- e Samples of approximately 4 mL will be collected.
- f In addition to the scheduled immunogenicity sampling, in the event of an infusion-related reaction, samples are to be collected as close to the onset of the event as possible, at the resolution of the event, and 28 days following the event.
- g Time-matched baseline ECGs (triplicates) will be taken within 4 days prior to Day 1 of Cycle 1, at the planned time for pre-infusion of olaratumab, immediately postinfusion of olaratumab (approx. 1 h after pre-infusion of olaratumab) and 1 h \pm 10 min postinfusion of olaratumab (approx. 2 h after pre-infusion of olaratumab) on Day 1.
- h If the second olaratumab administration in the cycle is delayed, olaratumab PK sampling and ECG will still be conducted at approximately 168 h postinfusion of olaratumab on Day 1. An additional olaratumab PK sample should then also be collected prior to the second olaratumab administration in the cycle.
- i If the second olaratumab administration in the cycle is delayed, the specified olaratumab PK sampling and ECG will be conducted based on the day of the second olaratumab administration in the cycle.

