6.2. Adjustments for Covariates

Adjustments for covariates will not be performed in any analysis of this study.

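### The concentration-QTc regression in SAP 6.11.7.1 plots a 90% interval without saying how repeated ECGs from one patient are handled; separately, the planned dose intensity in SAP 6.11.1 does not fit Cohort 3

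*SAP*

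**What the plan says.** SAP 6.11.7.1 plots time-matched QTc changes against olaratumab concentration by part and cohort: "A linear regression model will be used to investigate the relationship between the QTc changes and the concentration of olaratumab". The fitted model and a 90% interval go on the plot. The SAP does not say whether the interval is for the mean line or for something else.

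Two other passages bear on repeated data. SAP 6.11.7 takes three ECGs at each time point and says "The average of them will be used for analysis, if applicable", which deals with replicates at one time but not with the many times per patient. SAP 6.2 says "Adjustments for covariates will not be performed in any analysis of this study".

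The baselines are in footnote g of protocol Attachment 4. In Part B, "Time-matched baseline ECGs (triplicates) will be taken within 4 days prior to Day 1 of Cycle 1", at three planned times. For Cohorts 2 and 3 there are two, "at the planned time for pre-infusion of olaratumab and 1 h ± 10 min postinfusion of olaratumab". On size, protocol 10.1 says "The study design requires 6 patients at each cohort in Part A", and Part B also has 6.

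SAP 6.11.1 sets planned olaratumab intensity at 10 mg/kg/week for every patient. Protocol 7.2.1.1 gives Cohort 3 a 20 mg/kg loading dose on both dosing days of Cycle 1. Protocol 10.4 summarises relative dose intensity by part and cohort.

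The SAP is Version 1, approved 04-Mar-2015 for the two-cohort protocol. Cohort 3 came with Amendment (a), approved 26 Jun 2015.

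**The concern.** Changes from baseline that subtract the same reading carry the same baseline error, so they are correlated even if patients do not otherwise differ. Ordinary regression treats each pair as a separate piece of information and therefore overstates precision. The plotted interval is the only precision statement planned for the concentration-QTc relation, and an interval that is too narrow understates the uncertainty about QTc prolongation.

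The dose-intensity point is smaller. With a denominator of 10, Cohort 3 would appear dosed above plan beside Cohort 2, and missed Cohort 3 dosing could be hidden behind a reading near 100%.

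A third, minor point is that the first doxorubicin ECG exclusion names one cohort only ("in Cohort 2 of Part A, ECG data at the sampling time of" half an hour after doxorubicin). The second ("Especially when olaratumab and doxorubicin will be administered on Day 8 in Cycle 3, additional sampling times") names none but follows from the first. Attachment 4 gives Cohorts 2 and 3 the same schedule.

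**Working it through.** **Pairs per patient (Attachment 4, through Cycle 5).** Part B has 36 times with both an ECG and an olaratumab sample. Its table is partly broken in the text supplied, and 36 is the count that fits its sample numbering. Cohorts 2 and 3 have 15, because the ECG at 0.5 h after doxorubicin has no olaratumab sample. Cohort 1 is not counted because its table is too broken.

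**Correlation from shared baselines.** Let every averaged reading have error variance s². Then Var(post − base) = 2s², and two changes sharing a baseline have covariance s², so r = s²/2s² = 0.5. The SAP does not say which baseline serves the 24 to 168 h ECGs. If it is the pre-infusion one, the baseline groups are 22/10/4 in Part B and 13/2 in Cohorts 2 and 3. The average pairwise correlation is:

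- Part B: 0.5 × (22×21 + 10×9 + 4×3)/(36×35) = 0.5 × 564/1260 = 0.22
- Cohorts 2 and 3: 0.5 × (13×12 + 2×1)/(15×14) = 0.5 × 158/210 = 0.38

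**Simulation inputs.** No true effect; 2000 to 6000 runs per case. From protocol 5.4.4: half-life 6.7 days and a steady-state peak of 380 µg/mL, inside the reported 341 to 411. Assumed: one-compartment decline, and concentration CV of 25% between patients and 10% residual. Coverage is scale-free, so no QTc SD is needed. The line is evaluated at peak (380 in Part B and Cohort 2; about 447 in Cohort 3 after the loading dose) and at the median scheduled concentration (239, 163 and 185). For Cycle 1 alone the peaks are 337, 335 and 447.

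Coverage of the nominal 90% interval under ordinary regression:

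| Case | Part B | Cohort 2 | Cohort 3 |
|---|---|---|---|
| 6 patients, peak | 55% | 73% | 73% |
| 6 patients, median | 41% | 47% | 46% |
| Cycle 1 pairs only (13 or 7), peak | 78% | 82% | 82% |
| 3 of 6 stop after Cycle 1, peak | 58% | 76% | 76% |
| 12 patients, peak | 56% | 74% | not run |

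Averaging one fitted line per patient, with a t interval on (patients − 1) df, covers 89% to 92% in all of these cases.

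**Checks and sensitivity at 380 µg/mL.** With independent pairs, ordinary regression covers 90%, as it should. If one baseline reading serves every ECG (r = 0.5 throughout), it covers 37% in Part B and 61% in Cohort 2. With an assumed within-patient correlation of 0.1 to 0.6 instead, it covers 66% down to 33% and 82% down to 57%, while averaged per-patient lines cover 89% to 91%.

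**Dose intensity.** The SAP figure reproduces for the regimens in Version 1: 15 × 2/3 = 10 mg/kg/week. The doxorubicin figure fits all three cohorts: 75/3 = 25 and 3 × 25/3 = 25 mg/m²/week. Cohort 3 plans 2 × 20/3 = 13.3 mg/kg/week in Cycle 1. Over k cycles, a fully dosed Cohort 3 patient reads (40 + 30(k−1))/(30k):

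| Cycles | Reading when fully dosed | Share of plan received at a reading of 100% |
|---|---|---|
| 1 | 40/30 = 133% | 30/40 = 75% |
| 2 | 70/60 = 117% | 60/70 = 86% |
| 6 | 190/180 = 106% | 180/190 = 95% |

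**The case against.** The SAP does not say ordinary least squares on independent points, and a mixed model is also a linear regression. That is fair: the method is unspecified, and every coverage figure is conditional on the plain reading. But nothing in the text points to a patient term, and SAP 6.2 makes one harder to read in.

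The SAP refers to the time-matched baseline for Cycle 1 and does not map later ECGs to a baseline reading. If only Cycle 1 changes are regressed, coverage at peak is 78% to 82%, which is still short. The exclusions in the same section name Cycle 3, which favours the wider reading. Under any mapping there are only three or two baseline times to share.

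The assumed concentration profile is not exact. It implies a steady-state trough of 380 × 2^(−14/6.7) = 89 µg/mL, against 113 to 121 in protocol 5.4.4. A half-life of 8.5 days moves coverage by at most about 3 points.

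SAP 6.1 plans pharmacokinetic analyses elsewhere, so pairing rules may exist in a document not supplied. That could settle the pairing, but the regression and its interval are specified in this SAP.

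The strongest objection concerns weight. This is a supportive plot with no QTc margin or decision rule, and the categorical QTc counts do not depend on it. The dose-intensity and exclusion points arise only because the SAP predates Amendment (a). All of that stands, and it limits the importance of the point without removing it. The missing within-patient method was already a gap for the two-cohort design.

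**Conclusion.** The concern holds. If the regression is fitted as ordinary least squares, the plotted 90% interval covers roughly 55% to 73% at peak and 41% to 47% at the median concentration. These figures rest on equal error variance for baseline and later readings, the assumed baseline matching, and the assumed concentration profile and variability. They include no patient-to-patient QTc differences beyond the shared baselines. Enrolling more patients does not cure the problem.

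The 10 mg/kg/week denominator is exact for the regimens in Version 1 and wrong for Cohort 3, with an error that shrinks from 33 points at one cycle to 6 at six cycles. It does not touch the DLT decision: under protocol 7.2.1.3, toxicity requiring a Cycle 1 reduction or omission is itself a DLT, and reductions and omissions are listed separately. The exclusion wording matters in practice only for the four Cycle 3 Day 8 times when both drugs are given that day.

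The regression should be corrected. The other two points are updates needed because of Amendment (a). Confidence is medium, because a later SAP version may already deal with some or all of this.

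**What to change.** In SAP 6.11.7.1, fit one line per patient, average the lines, and plot the averaged line with a 90% t interval on (patients − 1) df. Use the same method for any slope reported. State what the interval is for, how each ECG is paired with a concentration and a baseline time, and the minimum number of pairs for a patient to be fitted. State also that this is not a covariate adjustment under SAP 6.2, and that both doxorubicin exclusions apply to Cohort 3. A mixed model with a patient effect would also answer the gap; averaged lines are simple and held their coverage here.

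In SAP 6.11.1, take the Cohort 3 planned intensity from the protocol's own schedule: (40 + 30(k−1))/(3k) mg/kg/week over k cycles. Issue these changes as a SAP version citing Amendment (a), or confirm that a later version already contains them.

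The cost is wording and a few lines of code. Under shared baselines the interval becomes about 1.7 (Cohorts 2 and 3) to 2.9 (Part B) times wider at peak, and 3.0 to 3.7 times wider at the median. If there were no correlation at all, it would be 1.4 to 1.5 times wider at peak than needed. The interval rests on few patients, and a patient with few ECGs counts as much as one with many.
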